Number of Subjects	Enrollment:120[anticipate]
	PBC group: 60[anticipate]
	Healthy group:60[anticipate]
Enrollment Criteria	Inclusion criteria were:
	(1) All patients were PBC older than 18 without any cardiac symptoms.
	(2) The diagnosis of PBC was established when patients met at least two of three
	criteria:
	1) elevated alkaline phosphatase or γ -glutamine transpeptidase;
	2) positive anti-mitochondrial antibodies (AMA) or specific antinuclear antibody
	(ANA) (sp100, gp210) positive;
	3) histological findings of chronic and non-suppurative inflammation, which
	surrounds and destroys interlobular and septal bile ducts.
	Exclusion criteria were :
	(1) having cardiac discomfort or a prior history of heart disease, abnormal
	electrocardiographic results; stress echocardiography proved wall motion
	abnormality, coronary CT or angiography proved coronary artery stenosis >50% when
	Framingham risk score was over 10.
	(2) having cirrhosis or other known liver diseases such as viral hepatitis, alcohol-
	induced liver injury, drug-induced liver injury, and inherited metabolic liver disease.
	(3) life expectancy of less than 6 months due to any condition.
	(4) for magnetic resonance safety reasons: standard metallic contraindications to
	CMR, or severe infection and renal failure (i.e., an estimated glomerular filtration rate
	< 30 ml/min/1.73 m2);
	(5) patient with any medical conditions that in the opinion of the investigators will
	not be appropriate to participate in the study.
Safety Assessments	Participants will be assessed for AEs at scanning while on the study. Adverse events
	will be graded according to the CTCAE v4.03. Type, incidence, severity, timing,
	seriousness, and relatedness of AEs and laboratory abnormalities will be reported.
Endpoints	1.LGE and T2-STIR
	2.ECV mapping
Statistical Analysis	Continuous variables are expressed as median (quartile) and categorical variables
	as numbers and percentages. Ventricular volume was acquired by both
	echocardiography and CMR; the latter was used for analysis. For continuous
	variables, the Mann-Whitney U test was used to compare between two groups.

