Categorical variables were compared using the Pearson's chi-squared test or Fisher's exact test. Logistic regression was used to identify the predictors of elevated ECV. Variables with P value <0.1 in univariable analyse were included into multivariable anaylse. Comparisons of variables between controls and PBC groups were adjusted for age and body surface area with covariance analysis. The interobserver reproducibility of CMR measurements was assessed using the interclass correlation coefficient (ICC), as well as intraclass coefficient analysis. The methods of sample size calculation could be found in supplementary materials. Statistical analysis was performed primarily using the SPSS 20.0 (SPSS Inc, Chicago, IL) system. P<.05 was statistically significant.

Sample Size Calculation. This study aimed to explore clinically silent myocardial impairments in PBC patients without presenting any reported cardiac clinical manifestation. According to previous CMR studies 3,4, ECV is one of the most valuable and sensitive indices reflecting myocardial change. In our pre-test including 10 PBC and 10 controls, the mean of ECV was 30% and 24%, respectively. The standard deviation of ECV in the entire group was 0.3. A margin of 4% was expected to differentiate between PBC and controls group. On the basis of margin and sample ratio (nPBC/nControl=1) and a type I error (two-side) of 5% and a power of 0.8, the final sample size required at least 42 subjects in each group.

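### The 42 per group in the sample size calculation does not follow from its stated inputs, and the stated SD of 0.3 does not fit the stated means, so the claimed 80% power is unsupported

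*Combined protocol and SAP*

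**What the plan says.** The paragraph headed Sample Size Calculation, in the combined protocol and SAP, rests the sample size on ECV, which is both a primary objective and a listed endpoint. Its inputs and result are:

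- Pre-test: "In our pre-test including 10 PBC and 10 controls, the mean of ECV was 30% and 24%, respectively".
- Spread: "The standard deviation of ECV in the entire group was 0.3", with no unit.
- Effect: "A margin of 4% was expected to differentiate between PBC and controls group".
- Error rates and allocation: "a type I error (two-side) of 5% and a power of 0.8", with "sample ratio (nPBC/nControl=1".
- Result: "the final sample size required at least 42 subjects in each group".

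The paragraph names no formula or test and gives no allowance for dropout or for a rank test. The Statistical Analysis section plans Mann-Whitney for two-group comparisons of continuous variables, and covariance analysis adjusted for age and body surface area for PBC against controls. It also refers to supplementary materials for the sample size methods. The Number of Subjects row plans more than 42: "PBC group: 60[anticipate" and the same number of healthy controls.

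**The concern.** All the inputs for a standard two-group comparison of means are printed, so 42 should be reproducible from them. It is not. The SD is the suspect input. It has no unit, it is described as the SD of the whole pre-test sample and not of each group, and it is hard to square with two group means 6 points apart.

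This is the only power statement in the documents. If it cannot be reproduced, a reader cannot tell whether the study has little power for a 4-point ECV difference or far more than it needs. Nor does the plan state the power at 60 per group, the number it intends to enrol.

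**Working it through.** **Formula.** For two equal groups, two-sided 5% and 80% power, the normal approximation is n per group = 2 × (1.960 + 0.842)² × SD² / d² = 15.70 × SD² / d², with SD and d in ECV percentage points. Values in brackets are from the noncentral t distribution.

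**Attempt to reproduce 42 with d = 4:**

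| Reading of 0.3 | SD (points) | Calculation | n per group |
|---|---|---|---|
| Fraction | 30 | 15.70 × 900 / 16 | 883 (884) |
| Percentage points | 0.3 | 15.70 × 0.09 / 16 = 0.09 | formula minimum of 1 (2) |
| Slip for 0.03 | 3 | 15.70 × 9 / 16 = 8.8 | 9 (10) |

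**Other differences.**

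- The full pre-test difference, d = 30 − 24 = 6: SD 30 gives 393 and SD 3 gives 4.
- The 4% taken as a margin to be exceeded when the true difference is 6, so net d = 2: SD 3 gives 15.70 × 9 / 4 = 35.3, so 36 (37). SD 30 gives 3,532.

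**Other readings of 0.3, with d = 4.** As a variance it gives 1 per group, and as a standard error 1 to 2. As a coefficient of variation applied to means of 24% to 30% it gives 51 to 80. As a standardised effect it gives 175. A one-sided 5% test gives 696, 1 and 7 for SD 30, 0.3 and 3. None of these is 42.

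**SD that 42 would require.** Solving the formula for SD gives d / (2.802 × √(2/42)) = d / 0.611. That is 6.5 points for d = 4, 3.3 for d = 2 and 9.8 for d = 6. The document states none of these.

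**Check of the SD against the means.** With ten subjects at a mean of 30 and ten at 24, every subject's group mean lies 3 points from the overall mean of 27. Even with no variation inside either group, the whole-group SD is √(20 × 3² / 19) = 3.08 points. If the true means were as close as 29.5 and 24.5 before rounding, the floor is √(20 × 2.5² / 19) = 2.56 points. So:

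- A whole-group SD of 0.3 points is arithmetically impossible.
- A whole-group SD of 3 points sits at the floor and leaves little spread within groups.
- A whole-group SD of 30 points is possible but is at least as large as either group mean.

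**What this does to power for a 4-point difference:**

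| SD (points) | Power at 42 per group | Power at 60 per group |
|---|---|---|
| 30 | 9% | 11% |
| 6.5 | 80% | 92% |
| 3 | above 99.9% | above 99.9% |

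**The case against.** The best defence is that a reasonable calculation lies behind the garbled text. Suppose 0.3 is a slip for 0.03 and the 4% is a margin set against the 6% pre-test difference. The formula then gives 35.3, or 36 per group. A 15% loss allowance gives 35.3 / 0.85 = 41.6, hence 42. Dividing 36 by 0.864, the worst-case efficiency of the planned Mann-Whitney test, gives 41.7, also 42. This may be what was done, but it needs a tenfold change to the printed SD, a use of the margin that the text does not describe, and an inflation that the text does not mention. The efficiency route also depends on rounding up first, since 35.3 / 0.864 = 40.9 gives 41. It is a conjecture and does not reproduce the calculation.

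Other points on that side have some force:

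- The SD may loosely mean a pooled within-group SD. In that case 3 points would not conflict with the means. The text does not say so, and SD 3 with a 4-point difference still gives 9 to 10.
- Using a whole-group SD is conservative, because it contains the group difference and so raises n. That is correct. It is the wrong quantity for the formula, but that error alone would not cost power.
- The supplementary materials may give the formula or a loss allowance. They cannot make 0.3 points compatible with means of 30 and 24, and the paragraph is itself presented as the calculation.
- The study describes its aim as exploratory and plans 60 per group. This limits the practical harm, but it does not correct the stated figures.

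**Conclusion.** The concern holds. No reading of the stated inputs gives 42 per group without assumptions that the document does not state. The printed SD is impossible in percentage points, implausible as a fraction, and does not lead to 42 as a slip for 3 points.

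The consequence is that 80% power for a 4-point ECV difference is not shown; the study is not shown to be underpowered. Using the t-test, 60 per group keeps 80% power for 4 points up to a within-group SD of about 7.7 points, so the planned enrolment may well be adequate.

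These figures take the 4% and the means as ECV percentage points and assume equal groups, a common SD, and a two-sided comparison of means at 5%. The floor on the SD needs only the two pre-test means, the group sizes and the literal reading that the SD covers the whole pre-test sample. The sole sample size justification is wrong as written, so it must be corrected.

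**What to change.** Rewrite the Sample Size Calculation paragraph to:

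1. Replace 0.3 with the pre-test within-group SD of ECV, in percentage points, and label it as within-group.
2. State whether 4% is the difference to be detected or a margin beyond which superiority is claimed. If it is a margin, state the assumed true difference.
3. Name the formula and test, with any allowance for loss or for the Mann-Whitney test, and recompute the number per group.
4. State the power for the 60 per group actually planned.

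If the pre-test SD cannot be recovered, report the detectable difference at 80% power instead: 0.52 within-group SD at 60 per group, or 0.62 at 42. These are t-test values. Under normality the planned Mann-Whitney test needs about 0.53 and 0.63, so the text should say which test the figure refers to.

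The cost is one corrected paragraph. The planned 60 per group can stay, and no extra patients or procedures are needed for the correction.
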